2.3.2 Secondary Efficacy Analyses

Secondary efficacy outcomes are the following:

1. Change from baseline in echocardiographic parameters including RV/LV ratio, TAPSE, estimated RVSP, and collapse of the IVC with respiration within 4 hours of the end of the APT procedure,

24 and 48 hours after start of the APT procedure, 30 days, 90 days and 365 days after the APT procedure (procedure start date = Day 0)

2. Change from baseline in thrombus burden by modified Miller score as assessed by CTA at 48 hours after the start of the APT procedure
3. Freedom from major harm occurring between enrolment and 30 days and assessed by the Safety Monitor using the following criteria:
 - a. Mortality – all cause and PE related
 - b. CV collapse: Defined as one or more of the following:
 - i. >40mmHg drop in SBP (for >15 minutes from documented blood pressure as an in-patient) despite IV fluid challenge and absence of new atrial arrhythmia.
 - ii. Requirement for emergency systemic thrombolysis
 - iii. Requirement for emergency surgical embolectomy
 - iv. Requirement for vasopressors
 - v. Intubation/Ventilation
 - c. Major bleeding per ISTH
 - d. Recurrent PE (confirmed by imaging)
 - e. Surgical correction of device related complication
4. 6 minute walk (6MW) distance with BORG score and requirement for oxygen therapy at 30 days, 90 days and 365 days, and changes from 30 days
5. Quality of life (QOL) as measured by the Pulmonary Embolism Quality of Life (PEmb-QOL) and EuroQual - 5 Dimensions – 5 Levels (EQ-5D-5L) at all post-hospitalization subject visits and phone contacts.
6. Healthcare resource utilisation during hospitalisation:
 - a. Time from hospital admission to diagnosis of PE
 - b. Time from diagnostic CT scan to initiation of treatment for PE
 - c. Time in each Level of Care (Level 0 and 1; Level 2; and/or Level 3) through discharge. Levels are defined according to National Framework Document.
 - d. Team managing the pt – specialties involved
7. Healthcare resource utilisation after hospitalisation and during first 12 months:
 - a. Team managing the pt - specialties
 - b. HCP visits for VTE
 - c. Hospital re-admission frequency and duration

For continuous efficacy endpoints, n, mean, standard deviation, median, minimum, and maximum will be provided at baseline and all appropriate follow-up timepoints. Changes from baseline (absolute change and percent change) will be similarly summarized at all follow-up time points with 95% confidence intervals for mean changes. Statistical significance for changes from baseline will be assessed by t-test. In addition,

combining data over 4 hours, 24 hours, 48 hours, 30 days, 90 days and 365 days post APT procedure, mixed model repeated measures (MMRM) analyses will be performed for all echocardiogram absolute and percent changes from baseline measures (RV/LV ratio, TAPSE, and RVSP). The baseline value, unilateral vs. bilateral PE indicator, and time point indicators will be included in the model as covariates in all cases.

For IVC collapse (with respiration) changes from baseline, the data will be summarized as 2×2 tables for paired binary data at each follow-up time point. The statistical significance will be assessed by the exact McNemar's test.

The above secondary analyses will be performed for the **ITT Subject Set**.

Lastly, as for the primary endpoint of RV/LV ratio decrease from baseline, an increasing benefit trend from treatment groups 1 through 3 will be explored for echocardiogram endpoints (RV/LV ratio, TAPSE, and RVSP at all six timepoints), and modified Miller score (at 48 hours) for changes from baseline. The analyses will be the same as that for the primary RV/LV ratio analysis and will be performed for the **ITT Subject Set**.

2.4 Safety Analysis

Safety analyses will be performed for the **Safety Subject Set**.

For the primary safety analysis, the number and percentage of subjects with major bleeding events within 72 hours of start of APT procedure will be reported with a 95% Wilson confidence interval.

Secondarily, the frequencies and proportions of subjects with technical procedural complications, symptomatic recurrent PE, and all cause mortality through the 365 day follow-up period will be reported with 95% Wilson score confidence intervals.

In addition, adverse events experienced through 30 days and SAEs through 365 days will be mapped to standard terms and summarized. For a given event, the frequency and proportion of subjects reporting it will be tabulated according to the worst severity experienced. Two separate tables will be constructed for each a) all reported events, b) events related to interventional procedure (not EKOS system), c) events related to EKOS system, d) events related to thrombolytic drug, e) events related to anticoagulant drug, f) bleeding events (3rd table will be constructed through 72 hours), and g) SAEs.

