Placement of the EKOS catheter will be guided by focused PAgm and/or CTA scan. Following successful placement of the EKOS catheter, the APT Procedure will be initiated with r-tPA and the ultrasound started simultaneously. Within four hours after the end of the APT Procedure, subjects will have an echocardiogram obtained. A repeat CTA will be obtained at 48 hours (± 6 hours) after the start of the APT Procedure. Echocardiograms will be obtained at 24 hours (± 6 hours) and at 48 hours (± 6 hours) after the start of the APT Procedure. Vital signs and hemodynamic measurements will be recorded as specified in Sections 7.4 and 7.5.

Integrated bedside assessments will only be obtained at select participating institutions by collecting vital signs and limited echocardiograms (RV/LV ratio only) at frequent intervals from the start of the APT Procedure through 4 hours after its completion to evaluate the possibility of developing a non-invasive PE response evaluation tool for use at the bedside (see Section 7.8). This collection of vital signs and echocardiograms will be reviewed to determine if there is a correlation with the change in clinical parameters and the change in markers of RV strain. The collection of routine bedside vital signs and limited echocardiograms (RV/LV ratio only) do not increase the potential risk to the patients participating in the study. They are non-invasive measurements that will be collected at a higher frequency than normal.

Bleeding, recurrent PE and serious adverse events will be collected and reported throughout the study. Specific reporting for bleeding events will occur during the first 72 hours from the start of treatment or at the time of discharge from the hospital, whichever is earlier.

All imaging studies will be provided to the Core Imaging Laboratory. Procedures for transfer of images from study sites to the Laboratory will be provided in the Syntactx Manual of Operations. Results of the assessments will be entered into the clinical database by the Core Imaging Laboratory.

Subjects will return for follow-up clinic evaluations at 30 (± 5 days), 90 (± 10 days), and 365 (± 14 days) days. It is imperative that contact with subjects be made at the designated times during the study and the status of all subjects is known at 365 days after the Procedure. Subjects will be asked to provide three different means of contact in order to insure an ability to learn the subject's status.

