6.10 Subject Withdrawal and Early Termination

Subjects may withdraw from participation at any time during the clinical study. All data collected prior to withdrawal will remain part of the study. Every effort will be made to have the subject return to the clinic to obtain final study assessments. If the subject declines, determine and document the reason for withdrawal.

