2 STATISTICAL ANALYSIS

2.1 Analysis Subject Sets and Missing Data Handling Convention

The **Intent-to-Treat (ITT) Subject Set** includes all randomized subjects; analyses will be performed for all primary and secondary efficacy endpoints for the ITT Subject Set. Unless otherwise specified, all available data will be used for ITT analyses regardless of whether the assessment timing is within the specified window.

The **Efficacy Evaluable (EE) Subject Set** includes randomized subjects who received the APT Procedure with EKOS treatment and for whom a CTA calculated RV/LV ratio is available at both baseline and 48 ± 6 hours from the beginning of the APT procedure. For the primary endpoint of CTA RV/LV ratio change from baseline to 48 ± 6 hours only, a subset analysis will be performed for EE patients in the ITT Subject Set. These analyses will only include data obtained in the pre-specified windows of (a) within 48 hours before APT start for baseline and (b) within ± 6 hours for 48 hours from APT start.

Safety Evaluable Subjects are defined as enrolled subjects for whom the APT Procedure was initiated, i.e. venous access attempted for EkoSonic catheter introduction, as indicated in database by a non-mising start time for EkoSonic placement (EXSTTM in the interventional procedure (EX) dataset). The **Safety Subject Set (SSS)** includes all safety evaluable subjects and will be used for all safety analyses.

Missing data will not be imputed for the efficacy and safety analyses.

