At select participating sites: In addition to the vital signs specified in Section 7.4, bedside vital signs including, systolic/diastolic blood pressure, heart rate, respiratory rate, capillary refill time and SpO2 will be recorded at the start of the APT Procedure, and at each 30 minute interval until 4 hours post-completion of the APT Procedure. Along with the echocardiograms specified in Section 7.7, limited echocardiograms performed at the bedside for RV/LV ratio measurements will be obtained hourly after the start of the APT Procedure through 4 hours post procedure.

Scatterplots of RV/LV ratio (y-axis) vs vital sign measures (x-axis) and of change in RV/LV ratio vs changes in vital sign measures will be presented to assess the correlation of change in clinical parameters (vital signs) with change in markers of RV strain (RV/LV ratio), and associated Pearson or Spearman correlation coefficients, where applicable.

Subject Set = Safety Subject Set for (19 – 23)

- 21) Major Bleeding Events within 72 hours of initiation of APT*
- 22) Technical Procedural Complications (*captured on the EkoSonic Device CRF as “Was this device successfully placed and used for treatment?”; make this a by-patient listing*)
- 23) Symptomatic Recurrent PE and Symptomatic Recurrent PE up to Day 365 (Confirmed by imaging)
- 24) All cause mortality up to Day 30 and all cause mortality up to Day 365 (*note: per AE and study exit CRFs*)
- 25) Adverse Events (*Run tables for AEs up to Day 30: AE start date ≤ Date of 30 Day Follow Up Visit per Follow-Up CRF*)
 - a) All reported events
 - b) Related to interventional procedure (not EKOS system)
 - c) Related to EKOS system
 - d) Related to thrombolytic drug
 - e) Related to anticoagulant drug
 - f) Bleeding events (*all site reported bleeding events, make tables for:*
-All reported bleeding events
-Those within 72 hours of APT start
-Those related to:
-interventional procedure (not EKOS system)
-EKOS system
-thrombolytic drug
-anticoagulant drug
 - g) SAEs

Also run analyses for (g) through Day 365, including those through 30 days.

26) Freedom from major harm occurring between enrolment and 30 days and assessed by the Safety Monitor using the following criteria:

- a. Mortality – all cause and PE related
- b. CV collapse: Defined as one or more of the following:
 - i. >40mmHg drop in SBP (for >15 minutes from documented blood pressure as an in-patient) despite IV fluid challenge and absence of new atrial arrhythmia.

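### One-year death and recurrent PE are planned as crude proportions of the full Safety Subject Set, which modestly understates both if subjects withdraw, and no table shows how many Day 365 outcomes are unknown

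*SAP*

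**What the plan says.** SAP 2.4 sets the analysis for technical complications, recurrent PE and death as frequencies and proportions of subjects, and continues: "symptomatic recurrent PE, and all cause mortality through the 365 day follow-up period will be reported with 95% Wilson score confidence intervals". Protocol 10.4 plans the same kind of summary.

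The denominator comes from SAP 2.1. The Safety Subject Set "includes all safety evaluable subjects and will be used for all safety analyses", and a subject is safety evaluable once venous access for the catheter has been attempted. No length of follow-up is required. The same section adds: "Missing data will not be imputed for the efficacy and safety analyses".

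SAP Appendix 1 lists the tables. Item 23 is "Symptomatic Recurrent PE and Symptomatic Recurrent PE up to Day 365", confirmed by imaging. Item 24 is "All cause mortality up to Day 30 and all cause mortality up to Day 365", with a note pointing to the AE and study exit forms. Neither item carries the asterisk that marks pooling with the earlier OPTALYSE PE subjects, so both rest on the UK Extension alone, where the SAP synopsis reports 29 enrolled. The line above these tables assigns the Safety Subject Set to items 19 to 23, which does not match the numbering below it, but SAP 2.1 and 2.4 put mortality on that set too.

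On follow-up, Protocol 6.10 allows withdrawal at any time, asks for final assessments where possible, and says: "All data collected prior to withdrawal will remain part of the study". Protocol 4 calls it imperative that "the status of all subjects is known at 365 days after the Procedure".

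**The concern.** A proportion over everyone who started the procedure is a one-year risk only if everyone is observed for one year. A subject who withdraws at Day 40 with no event adds to N but, unless later information is obtained, cannot add to n. In the arithmetic that subject is a non-event for the remaining 325 days. The rate is pulled downwards, and the Wilson interval treats the unknown outcome as an observed non-event.

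The one-year follow-up has a stated purpose. Protocol 1.2 gives it as information on VTE recurrence and on chronic thromboembolic pulmonary hypertension, so recurrent PE at one year is an outcome that readers will look for. Appendix 1 has no disposition or completion table from which they could judge how complete that information is. With three arms sharing 29 subjects, one or two withdrawals can visibly move an arm's percentage.

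**Working it through.** There is no plan figure to reproduce: neither document gives a one-year event rate or a withdrawal rate. Every rate below is an assumption, used to show the range.

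**Expected crude rate against true risk.** Let R be the true one-year risk and q the fraction withdrawn by one year. Assume a constant event hazard and withdrawal independent of outcome.

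- Event hazard: λ = −ln(1 − R). Withdrawal hazard: μ = −ln(1 − q).
- Withdrawal spread over the year: crude = λ/(λ + μ) × [1 − exp(−(λ + μ))].
- All withdrawals at Day 30: crude = (1 − q)R + q[1 − exp(−λ × 30/365)].

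Example with R = 5% and q = 20%: λ = 0.0513, μ = 0.2231, and 1 − exp(−(λ + μ)) = 1 − 0.95 × 0.80 = 0.24. Crude = 0.0513/0.2744 × 0.24 = 0.0449, and 0.0449/0.05 = 0.90.

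| Withdrawn by one year | Crude ÷ true, spread over year | A true 5% appears as | Crude ÷ true, all at Day 30 |
|---|---|---|---|
| 5% | 0.975 | 4.9% | 0.95 |
| 10% | 0.95 | 4.75% | 0.91 |
| 20% | 0.90 | 4.5% | 0.82 |
| 30% | 0.84 | 4.2% | 0.73 |

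The ratios are almost the same for true risks of 3% and 10%. The relative shortfall is 2.5% to 16% with withdrawal spread over the year, and up to 27% if 30% leave at Day 30.

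**Small-number cases** (counts assumed; about 10 per arm if the 29 are balanced):

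- 29 subjects, 3 withdrawn before a single late event: crude 1/29 = 3.4%; Kaplan-Meier 1/(29 − 3) = 1/26 = 3.8%.
- Arm of 10, 2 withdrawn before a single late event: crude 1/10 = 10.0%; Kaplan-Meier 1/8 = 12.5%.

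**Sampling error for comparison.** 95% Wilson intervals are 0.6% to 17.2% for 1/29, 1.8% to 40.4% for 1/10, and 0 to 27.8% for 0/10. The shifts above are small beside these widths.

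**The case against.** The strongest reply is that no such counting rule is written. The SAP does not say how subjects of unknown status are counted, and the no-imputation sentence could be read as dropping them. That stands as a limit: the full-set denominator is an inference, though the likelier one, because SAP 2.1 uses the full set for all safety analyses and defines no criterion for a missing Day 365 outcome. A reader might go further and infer that the SAP deliberately scores unknown as event-free, or that deaths after study exit can never be recorded. The documents do not support either. Item 24 names its source forms without excluding others, and Protocol 6.10 is silent on information obtained after withdrawal.

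Conduct provisions also help. Protocol 4 asks for three means of contact, Protocol 6.7 recommends that they include a next of kin or close associate, and Protocol 8.6 collects serious events including VTE to Day 365. These should recover most deaths. They help less with recurrent PE, which needs documented symptoms or signs plus imaging. They are conduct aims and do not supply an analysis rule. Some attrition will show in the numbers reported by visit for echocardiography, walk test and quality of life, but those numbers do not count unknown vital or VTE status.

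A reader might also build a worst case: with 2 deaths and 5 unknown among 29, the plan gives 6.9% (Wilson 1.9% to 22.0%), while all five dying would give 7/29 = 24.1%. The counts are invented and the bound is extreme. The known-status figure in the same example is 2/24 = 8.3%, well inside the interval. Nor does SAP 2.4 plan a between-arm safety test that unequal withdrawal could distort.

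**Conclusion.** The point holds as a modest one. On the natural reading of SAP 2.1 and 2.4, one-year mortality and recurrent PE are biased downwards by withdrawal, and the listed tables do not show how many Day 365 outcomes are unknown. The crude rate would be about 0.975 to 0.84 of the true risk for an assumed 5% to 30% withdrawal spread over the year, and lower if withdrawals come early. This rests on a constant hazard, on withdrawal unrelated to outcome, and on all safety evaluable subjects staying in the denominator.

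These are secondary descriptive outcomes, and at 29 subjects sampling error exceeds the likely bias. The effect is larger for recurrent PE than for death, since vital status can be obtained by contact. It would be wrong to conclude that the planned rates are seriously misleading or that their intervals are invalid. The case for change is that a better estimate and a count of unknown outcomes can be added cheaply without removing anything planned.

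**What to change.** In SAP 2.4 and Appendix 1 items 23 and 24, keep the crude n/N with its Wilson interval, state who is in the denominator, and add beside it:

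- the number of subjects with known and with unknown Day 365 status, by arm;
- a Kaplan-Meier estimate of one-year mortality, and a cumulative incidence of recurrent PE with death as a competing event, both censored at last known status, for all UK patients together and descriptively by arm.

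Two details need writing in. Treat a completed Day 365 ± 14 visit as full follow-up; otherwise a completer seen on Days 351 to 364 would be censored before Day 365. Where an arm has no events, report the Wilson interval, because the Greenwood interval then has zero width. If nobody is censored, both added estimates equal n/N.

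The cost is a little more analysis. Serious-event onset dates are collected, and a study exit form exists (that it carries a date is assumed). The SAP is dated November 2019 and enrolment ran to March 2019, so the last subjects had not reached Day 365 when it was written. Stated rates may be slightly higher, and the added estimates assume that withdrawal is non-informative. Changing Protocol 6.10 to seek Day 365 status from records after withdrawal is optional: it is an amendment and depends on what existing consent allows.

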2.5 Sample Size And Power Estimation

The primary efficacy endpoint for the study is the 48-hour decrease in RV/LV ratio. The Fasullo¹ study's heparin arm indicated a mean RV/LV ratio decrease of 0.20. Based on these results, we propose a mean

48-hour RV/LV ratio (absolute) decrease ≤ 0.20 as the null hypothesis for this study. Rejecting the null hypothesis with a 1-sided $p<0.15$ by t test will be regarded as a positive sign for further investigating a treatment regimen. For submassive PE subjects in the SEATTLE II study, a mean RV/LV ratio reduction of 0.43 was observed with a standard deviation of 0.41. Should these results be true for a regimen in the current study, with 25 evaluable subjects, the power to detect a positive signal is approximately 0.96.

The simultaneous power for the three treatment groups at the planned sample size of with $n=25$ evaluable per arm is approximately 0.88 by the Hochberg procedure².

Appendix 1: List of Tables (All summaries and analyses will be by treatment arm for the UK Extension portion of the study unless otherwise specified. Except for RV/LV ratio analyses, all p values are 2-sided. Analyses that will be conducted for the combined portions of the study (OPTALYSE PE plus UK Extension) as well as for the UK Extension alone and are indicated by an asterisk.)

Subject Set = ITT for (1) – (20) Unless Otherwise Specified

- 1) Enrollment by Site
- 2) Demographics
 - a) Age
 - b) Weight
 - c) BMI
 - d) Gender
 - e) Ethnicity (Hispanic vs. not Hispanic)
 - f) Race
- 3) Clinical History and Risk Factors
 - (a) – (v) on *Clinical History and Risk Factors CRF*.
 - a) Hypercholesterolemia
 - b) Congestive Heart Failure
 - c) Hepatic Insufficiency
 - d) Renal Insufficiency
 - e) TIA or Stroke
 - f) Active Cancer
 - g) Diabetes
 - h) Hypertension
 - i) Tobacco use
 - j) $BMI \geq 30.0$
 - k) COPD
 - l) History of Cancer in Remission
 - m) Family History of VTE
 - n) Chronic Inflammatory Disorders
 - o) Acute Infectious Illness within 30 Days of signing ICF
 - p) Atherosclerotic Cardiovascular Disease
 - q) Currently taking a Hormonal Contraceptive or Replacement Therapy
 - r) Osteoarthritis of Either Hip or Knee
 - s) All co-morbid conditions under A25 of Clinical History and Risk Factors eCRF, i.e. Cerebrovascular Disease, Recent GI or GU Bleeding, Currently receiving oral anticoagulants, Recent (within 2 weeks) major surgery, Recent trauma (within 2 weeks), High Liklihood of Left Heart Thrombus, Acute Pericarditis, Subacute Bacterial Endocarditis, Hemostatic Defects, Significant Hepatic Dysfunction, Diabetic Hemorrhagic Retinopathy or Other Hemorrhagic Ophthalmic Conditions, Septic Thrombophlebitis or Occluded AV Cannula at Seriously Infected Site, Any other Condition in which Bleeding Constitutes a Significant Hazard
 - t) All hypercoagulables under A26 of Clinical History and Risk Factors eCRF, i.e. Anticardiolipin Antibodies, Antiphospholipid Antibody Syndrome, Lupus Anticoagulant, Activated Protein C

Resistance, Factor V Leiden Mutation, Prothrombin Gene Mutation (20210a), other (*make a listing for other hyperanticoagulables by arm*)

- u) All presenting signs and symptoms A30 of Clinical History and Risk Factors eCRF, i.e. Dyspnea, Tachycardia, Hypoxemia, Transient Hypo-or Hypertension (treated by medications), Prolonged hypotension (> 15 minutes) requiring pressors to maintain adequate systolic pressure (exclude patient), Cardiogenic shock that has since resolved, Dizziness/lightheadedness, Syncope (fainting), Chest pain, Cyanosis, Tachypnea, Swollen upper extremity, Swollen lower extremity, Limb edema, Leg pain, Difficulty walking, Deep vein thrombosis confirmed by ultrasound scanning, Other (*make a listing for other presenting signs/symptoms by arm*)
- v) Inferior Vena Cava Filter Currently Present
- w) Platelet count <100,000 (Baseline labs)
- x) Heparin-induced thrombocytopenia (Inclusion/Exclusion B6)
- y) Pharmacomechanical treatment within 3 days (Inclusion/Exclusion B7)
- z) Venous Thromboembolism History (*Venous Thromboembolism History CRF*)
 - a) Type

4) Anticoagulation Medication by Visit

Make table by arm with (a) total N, (b) n/% subjects taking no anticoagulant meds, (c) n/% subjects taking any anticoagulant meds. Then under (c): n/% subjects taking each anticoagulant listed in A1 of the Anticoagulation Medication (acm) CRF

5) Baseline CT scan

- a) Locations of PEs
- b) Number of locations per patient with (a) any occlusion, partial or total, (b) partial occlusion, (c) total occlusion (n, mean, std, median, minimum, maximum)

6.1) Vital Signs

At screening/Baseline, start and end of the APT procedure, within 4 hours of end of APT procedure and 24 hours, 48 hours, 30 days, 90 days, and 365 days after the start of the APT procedure:

- a) Systolic BP
- b) Diastolic BP
- c) Heart Rate
- d) Respiratory Rate
- e) SpO2
- f) Oxygen Source

For each of (a) through (e), summarize as n, mean, standard deviation, median, minimum, maximum at each time point; construct box/whiskers plots for all 7 timepoints in the same graph and connect means and medians. For (f), summarize as frequency and percent in the order of room air, nasal prongs, mask and intubated at each time point

6.2) Laboratory Data

- a) Hemoglobin
- b) Hematocrit
- c) Platelet
- d) aPTT
- e) PT

- f) INR
- g) Troponin
- h) D-dimer
- i) BNP/proBNP
- j) Lactate/Lactic Acid

For each of (a) through (f), summarize as n, mean, standard deviation, median, minimum, maximum at baseline, post procedure 1 (within 4 hours post treatment) and post procedure 2 (48 hours).

For (g) through (j), summarize as n, mean, standard deviation, median, minimum, maximum at baseline and post procedure (48 hours).

6.3) PESI/sPESI

Summarize as n, mean, standard deviation, median, minimum, maximum at baseline, post procedure 1 (within 4 hours post treatment), post procedure 2 (24 hours) and post procedure 3 (48 hours).

7) Interventional Procedure

- a) Access Site Location
- b) Ultrasound Imaging Used
- c) Number of Attempts Required to Gain Access
- d) Total r-tPA dose per patient

8) EkoSonic Device Information

- a) Number of Devices Successfully Placed and Used for Treatment per Patient (*table entries are numbers of patients*) (*A footnote will be added with total # devices which were not "successfully placed and used for treatment" with reasons.*)
- b) EkoSonic Device Placement Site (*table entries are numbers of devices*)

9) Thrombolytic Infusion Details (by device used)

- a) r-tPA concentration (mg/mL)
- b) r-tPA infusion rate (mg/hr)
- c) Duration of r-tPA infusion (hrs)
- d) Reason for Infusion termination (completed per protocol, AE, or other)
- e) Deviations from prescribed therapy and reason (Protocol Deviation CRF, include all deviations with “APT Procedure not Performed as Prescribed by Protocol” checked)

10) EkoSonic System Details

- a) Duration of Ultrasound (hrs)
- b) Reason for ultrasound termination
- c) Deviations from prescribed therapy and reason

11) Core Lab RV/LV ratio from CTA: Baseline, 48 hours Post APT Start, absolute difference (Post-Procedure - Baseline) and percent change*

Summarize as continuous data for all above, i.e. n, mean, SD, median, minimum, maximum; provide 95% CI's for mean absolute and percent changes; provide 1-sided and 2-sided p values testing reduction ≤ 0.20 by t test for mean absolute change from baseline; provide same p values testing reduction ≤ 0 by t test for mean percent change from baseline.

All analyses above for RV/LV ratio by CTA will be repeated for the efficacy evaluable patient subset for ITT patients.

Lastly, repeat the above analyses for ITT patients as 6 arms, i.e. unilateral vs. bilateral for each of the 3 randomization arms.

Using continuous data from all 3 arms, perform increasing benefit trend analysis as described in the last paragraph of Section 2.3.1 and provide the 2-sided p value. (ITT only)

12) Core lab echocardiogram: Baseline, within 4 hours of APT end, 24 and 48 hours post APT start, Day 30, Day 90, Day 365 (procedure start date = Day 0) and change from baseline at all post-baseline time points (for continuous endpoints a-c below, besides summarizing as n, mean, SD, median, minimum and maximum at each of the 7 time points, also provide box-wisker plots for all time points on the same graph)*

- RV/LV ratio (perform same analysis at all time points as for the primary endpoint of RV/LV ratio as described in (11) above with the exceptions that testing a mean reduction of 0.20 applies to the 48 hours time point only and binary endpoint applies to \leq baseline vs. $>$ baseline only) (ITT)
- TAPSE (perform same analysis at all time points as for the primary endpoint of RV/LV ratio as described in (11) above, except mean absolute changes from baseline are tested against 0 as opposed to 0.20 and all p values are 2-sided and binary endpoint applies to \leq baseline vs. $>$ baseline only) (ITT)
- Estimated RVSP (perform same analysis at all time points as for the primary endpoint of RV/LV ratio as described in (11) above, except mean absolute changes from baseline are tested against 0 as opposed to 0.20 and all p values are 2-sided and binary endpoint applies to \leq baseline vs. $>$ baseline only) (ITT)
- IVC collapse with respiration (summarize as frequency and proportion at each time point and 2 \times 2 tables for changes from baseline, provide p values by McNemar's test) (ITT)

In addition: Combining data over 4 hours, 24 hours, 48 hours, Day 30, Day 90 and Day 365, perform mixed model repeated measures (MMRM) analyses for RV/LV ratio, TAPSE, and RVSP for absolute and percent changes from baseline as described in Section 2.3.2 (top of page 9). Provide the overall effect size estimate, 95% CI and 2-sided p value comparing effect to 0. (ITT)

15) Core Lab Modified Miller Score: baseline, 48 hours post APT, absolute and percent changes from baseline (CTA data, perform same analyses as for (14a) above) (ITT)*

16) QOL:

For QOL measures (PEmb-QOL total score, EQ-5D-5L Index value, EQ-5D-5L VAS), summarize as continuous endpoints by treatment arm for 30, 90, and 365 days. Include analysis of change over time for both assessments.

PEmb-QOL*

The PEmb-QOL questionnaire score ranges from 0 to 100. To score: Q1, Q4, Q5, and Q9 are to be reversely scored with a low score indicating a better quality of life. Two questions (Q2 'At what time of day are your lung symptoms most intense?' and Q3 'Compared to one year ago, how would you rate the condition of your lungs in general

now?') are not used for scoring. Item 4a will be considered missing if the answer was 'I do not work'. For a PEmb-QoL summary score, first transform each answered item score to a scale ranging from 0 to 100 (38 items total). Then average these transformed scores (except items Q2 and Q3) to obtain an overall summary score. No minimum was specified for the number of answered items. (Ref: Rochat et al. Health and Quality of Life Outcomes 2014, 12:174)

EQ-5D-5L*

The EQ-5D-5L is a self-administered questionnaire consisting of 5 questions pertaining to specific health dimensions (mobility, self-care, pain, usually activities and anxiety and depression), and health status rating scale (visual analogue scale [VAS]). Each dimension has 5 levels: no problems, slight problems, moderate problems, severe problems, and extreme problems. If a patient has died, the last EQ-5D-5L dimension assessment prior to death will be imputed as extreme problems (coded as 5) and flagged in the listing.

The VAS records the respondent's self-rated health on a 20 cm vertical, visual analogue scale with endpoints labeled 'the best health you can imagine' (Score=100) and 'the worst health you can imagine' (Score = 0). This information can be used as a quantitative measure of health as judged by the individual respondents. If a patient has died, the last EQ-5D-5L VAS assessment prior to death will be imputed as 0 and flagged in the listing.

Each one digit number expressing the level selected for each dimension can be combined into a 5-digit number describing the respondent's health state. For example, the number 11111 represents the respondent not having any problems in all five dimensions. These 5-digit numbers are health states which can be converted to an index value, where 1 represents full health and 0 is equivalent to death. A health state could be considered worse than death and the index values for those states will be less than 0. The index value will be calculated as:

Index value = 1 - (Dimension 1 Estimate + Dimension 2 Estimate + Dimension 3

Estimate + Dimension 4 Estimate + Dimension 5 Estimate). Each dimension estimate is based on the levels chosen for each dimension as specified in Appendix 2 Derivations

17) 6MW at 30, 90 and 365 days*

Summarize as n, mean, standard deviation, median, minimum, maximum at 30, 90 and 365 days. Also include analysis of change over time and between group comparisons.

18) Healthcare resource utilisation during hospitalisation:

- a. Time from hospital admission to diagnosis of PE
- b. Time from diagnostic CT scan to initiation of treatment for PE
- c. Time in each Level of Care (Level 0 and 1; Level 2; and/or Level 3) through discharge. Levels are defined according to National Framework Document.
- d. Team managing the pt – specialties involved

19) Healthcare resource utilisation after hospitalisation and during 12 month follow-up:

- a) Team managing the pt - specialties
- b) HCP visits for VTE
- c) Hospital re-admission frequency and duration

20) Rescue Therapies (*by patient listing sorted by arm with data for sub id, arm, and answers to items A1, A2, B1, B2, B3, B4, B5, B6, B7, C1, C2, C3 on the Rescue Therapy CRF*)

21) Protocol deviations

22) Integrated Bedside Assessment (IBA) – Only performed at one site with up to 13 subjects using dedicated eCRFs for data collection.

At select participating sites: In addition to the vital signs specified in Section 7.4, bedside vital signs including, systolic/diastolic blood pressure, heart rate, respiratory rate, capillary refill time and SpO2 will be recorded at the start of the APT Procedure, and at each 30 minute interval until 4 hours post-completion of the APT Procedure. Along with the echocardiograms specified in Section 7.7, limited echocardiograms performed at the bedside for RV/LV ratio measurements will be obtained hourly after the start of the APT Procedure through 4 hours post procedure.

Scatterplots of RV/LV ratio (y-axis) vs vital sign measures (x-axis) and of change in RV/LV ratio vs changes in vital sign measures will be presented to assess the correlation of change in clinical parameters (vital signs) with change in markers of RV strain (RV/LV ratio), and associated Pearson or Spearman correlation coefficients, where applicable.

Subject Set = Safety Subject Set for (19 – 23)

- 21) Major Bleeding Events within 72 hours of initiation of APT*
- 22) Technical Procedural Complications (*captured on the EkoSonic Device CRF as “Was this device successfully placed and used for treatment?”; make this a by-patient listing*)
- 23) Symptomatic Recurrent PE and Symptomatic Recurrent PE up to Day 365 (Confirmed by imaging)
- 24) All cause mortality up to Day 30 and all cause mortality up to Day 365 (*note: per AE and study exit CRFs*)
- 25) Adverse Events (*Run tables for AEs up to Day 30: AE start date ≤ Date of 30 Day Follow Up Visit per Follow-Up CRF*)
 - a) All reported events
 - b) Related to interventional procedure (not EKOS system)
 - c) Related to EKOS system
 - d) Related to thrombolytic drug
 - e) Related to anticoagulant drug
 - f) Bleeding events (*all site reported bleeding events, make tables for:*
-All reported bleeding events
-Those within 72 hours of APT start
-Those related to:
-interventional procedure (not EKOS system)
-EKOS system
-thrombolytic drug
-anticoagulant drug
 - g) SAEs

Also run analyses for (g) through Day 365, including those through 30 days.

26) Freedom from major harm occurring between enrolment and 30 days and assessed by the Safety Monitor using the following criteria:

- a. Mortality – all cause and PE related
- b. CV collapse: Defined as one or more of the following:
 - i. >40mmHg drop in SBP (for >15 minutes from documented blood pressure as an in-patient) despite IV fluid challenge and absence of new atrial arrhythmia.
 - ii. Requirement for emergency systemic thrombolysis
 - iii. Requirement for emergency surgical embolectomy
 - iv. Requirement for vasopressors
 - v. Intubation/Ventilation
- c. Major bleeding per ISTH
- d. Recurrent PE (confirmed by imaging)
- e. Surgical correction of device related complication

